## 6 VARIABLES IN THE CRF

The following groups of variables will be recorded for this observational study: Demographic data, medical history, first-line treatments, other treatments prior to axitinib, treatment with axitinib, subsequent treatments and the patient's vital status. Details of all the variables recorded in the CRF are given below:

- Demographic data:
  - Date of birth
  - Gender
- Clinical history of renal cell carcinoma
  - Date of first diagnosis
  - Tumour stage at disease diagnosis (I/II/III/IV)
  - Non-systemic treatment
    - Nephrectomy (Yes/No/Unknown).
      - If yes, specify:
        - Date (Date/Unknown)
        - Type (Total/Partial/Unknown)
        - Kidney (Right/Left/Unknown)
      - Radiotherapy (Yes/No/Unknown).
        - If yes, specify:
          - Date (Date/Unknown)
      - Histological type (100% Clear cells/ Primarily clear cells/ Primarily non-clear cells/ 100% Non-clear cells)
        - If 100% Clear cells have not been marked, specify (Sarcomatoid/Chromophobe/ type 1 Papillary/ type 2 Papillary/ Other, specify/Not performed)
    - Diagnosis of advanced disease
      - Date
      - Stage (III/IV)
      - Metastasis site (multi-response question):
        - Lymph nodes
        - CNS
        - Liver
        - Lungs
        - Bone
        - Other, specify
      - Risk criteria before the initiation of the first line
        - Time from initial diagnosis to systemic treatment less than 1 year (Yes/No/Unknown)
        - ECOG/PS (Yes/No/Unknown)
        - LDH >1.5 x ULN (Yes/No/Unknown)
        - Haemoglobin < LLN (Yes/No/Unknown)
        - Corrected calcium >10 mg/dl (Yes/No/Unknown)
        - Presence of 2 or more metastatic sites (Yes/No/Unknown)

- 
- Platelets > ULN (Yes/No/Unknown)
  - Neutrophils > ULN (Yes/No/Unknown)- (current value)
  - Lymphocytes (Yes/No/Unknown)- (value)
  - Smoking habits (Smoker/Non-smoker/Former smoker)
  - First-line treatment
    - Drug
    - Starting dose
    - Duration of treatment
      - Start date
      - End date
      - Reason for treatment withdrawal (DP/Toxicity/Other, specify)
      - Has there been disease progression? (No/Yes, specify date)
      - Best treatment response (CR, PR, SD, DP/Not evaluable).
        - Date of the best response obtained
  - Other treatments prior to axitinib
    - Has the patient received other treatments prior to axitinib? (Yes/No/Unknown)
      - If yes, specify:
        - 2nd-line treatment
          - Drug
          - Starting dose

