          - Reason for starting this treatment (DP in the 1st line treatment/Toxicity in the 1st line treatment/Other, specify)
          - Start date
          - End date
          - Reason for treatment withdrawal (DP/Toxicity/Other, specify)
          - Has there been disease progression? (No/Yes, specify date)
          - Best treatment response (CR, PR, SD, DP/Not evaluable).
            - Date of the best response obtained
        - 3rd-line treatment
          - Drug
          - Starting dose
          - Reason for starting this treatment (DP in the 2nd line treatment/Toxicity in the 2nd line treatment/Other, specify)
          - Start date
          - End date
          - Reason for treatment withdrawal (DP/Toxicity/Other, specify)
          - Has there been disease progression? (No/Yes, specify date)

- 
- Best treatment response (CR, PR, SD, DP/Not evaluable).
    - Date of the best response obtained
  - Treatment with axitinib
    - Treatment line in which it was received.
    - Reason for starting treatment with axitinib (DP in previous treatment line/Toxicity in previous treatment line/Other, specify).
    - Risk criteria at the initiation of treatment with axitinib
      - Time from first diagnosis to systemic treatment less than 1 year (Yes/No/Unknown)
      - ECOG/PS (current status) (Yes/No/Unknown)
      - LDH >1.5 x ULN (Yes/No/Unknown)
      - Haemoglobin < LLN (Yes/No/Unknown)
      - Corrected calcium >10 mg/dl (Yes/No/Unknown)
      - Presence of 2 or more metastatic sites (Yes/No/Unknown)
      - Platelets > ULN (Yes/No/Unknown)
      - Neutrophils > ULN (Yes/No/Unknown) (value)
      - Lymphocytes (Yes/No/Unknown) (value)
      - Smoking habits (Smoker/Non-smoker/Former smoker)
    - Presence of comorbidities
      - Kidney failure (Yes/No)
        - If yes, specify, Creatinine Clearance (Mild, 60-89 ml/min/ Moderate, 30-59 ml/min/ Severe, 15-29 ml/min/ End Stage, <15 ml/min/ Dialysis)
      - Liver failure (Yes/No)
        - If yes, specify, Child Pugh (A/B/C)
      - Cardiovascular (Yes/No)
        - If yes, specify (multi-response question)
          - Decreased LVEF, specify %
          - Heart failure
          - Previous arrhythmia
          - Previous ischaemia
          - Controlled HTN, specify number of antihypertensive agents
          - Other, specify
      - Respiratory disease (Yes/No), specify
      - Other comorbidity (Yes/No), specify
    - Start date of treatment with axitinib

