## 7 DEFINITION OF VARIABLES AND OBJECTIVES

In addition, the following variables will be calculated from the CRF data:

NOTE: In patients with dates after the date of the IC visit / signature, the date of the IC visit / signature has been considered as the date of the last check. Due to the retrospective nature of the study, no data can be collected after the patient was included in the IC study / signature.

- Age (years) of patient at time of visit= (Visit date – Date of birth) / 365.25
- Age (years) at first diagnosis= (Date of first diagnosis – Date of birth) / 365.25
- Age (years) at the initiation of axitinib= (start date of axitinib – Date of birth) / 365.25
- Number of metastatic locations = sum (Lymph nodes, CNS, Hepatic, Pulmonary, Bone, Other).
- • Neutrophil / lymphocyte ratio. It will be categorized as follows:  $\leq 3$ ,  $> 3$ . "Before the beginning of the first line" and "At the beginning of treatment with axitinib" will be analyzed. This ratio is not calculated on axitinib suspension because there is no current lymphocyte value data in that part of the CRF.
- Time (months) between first diagnosis and nephrectomy = (Date of nephrectomy – Date of first diagnosis) / 30.4375. A list with the information (site, patient, date of first diagnosis, date of nephrectomy and the calculated time) in cases in which the time is negative (with date of nephrectomy before or equal to date of first diagnosis) will be displayed, and these cases will not be included in the descriptive analysis
- Time (months) between first diagnosis and radiotherapy = (Date of radiotherapy – Date of first diagnosis) / 30.4375. A list with the information (site, patient, date of first diagnosis, date of radiotherapy and the calculated time) in cases in which the time is negative (with date of radiotherapy before or equal to date of first diagnosis) will be displayed, and these cases will not be included in the descriptive analysis.
- Time (months) between first diagnosis and 1st-line treatment = (Date of the initiation of 1st-line treatment – Date of first diagnosis) / 30.4375. A list with the information (site, patient, date of first diagnosis, date of 1st-line treatment and the calculated time) in cases in which the time is negative (with date of 1st-line treatment before or equal to date of first diagnosis) will be displayed, and these cases will not be included in the descriptive analysis

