- Duration of first-line treatment:([0-3] months, [3-6] months, [6-9] months, [9-12] months,  $\geq 12$  months).
- Duration of first-line treatment: ( $\leq 9$ months,  $>9$  months).
- Duration of first-line treatment: ( $\leq 12$ months,  $>12$  months).
- Duration of first-line TKi treatment: ([0-3] months, [3-6] months, [6-9] months, [9-12] months,  $\geq 12$  months).

It will be calculated the duration of the first line, if the drug was only a TKi.

- Duration of first-line TKi treatment: ( $\leq 9$ months,  $>9$  months).
- Duration of first-line TKi treatment: ( $\leq 12$ months,  $>12$  months).
- Duration of the first TKI treatment:( [0-3] months, [3-6] months, [6-9] months, [9-12] months,  $\geq 12$  months).

It will be calculated the duration of the first treatment with a TKi, in 1st or later line (always after axitinib).

- Patients treated with a TKi previous to axitinib other than first. It will be analysed the number of patients with a TKi previous to axitinib, different from the first TKi received.

It will be analysed the duration of this treatment.

- Best response with the TKI received in the first-line (CR, PR, SD, DP)
- Best response with a TKi previous to axitinib with a TKi other than first line (CR, PR, SD, PD).
- Best response with line prior to axitinib with a TKI if a line prior to axitinib other than the first one has been received (CR/PR, SD, DP).
- Number of metastatic locations (1, 2 and  $\geq 3$ ); See this definition in section 7 Definitions of variables and objectives.
- Site of metastases (CNS metastases [yes vs no]; lymph nodes [yes vs no]; lung [yes vs no]; liver [yes vs no]; bone [yes vs no]). In addition to showing the descriptive and comparative table of metastatic locations between groups, another similar table will be shown but with the categories “Hepatic” and “Bone” united in a single.
- Neutrophil/lymphocyte ratio  $\leq 3$  (yes vs no). See this definition in section 7 Definitions of variables and objectives. It will be analysed in all moments included in the study.
- Line of treatment in which it was received.

- 
- Presence of comorbidities.
  - Suspension of treatment.
  - Have you received any further treatment?
  - Has there been disease progression?
  - Best response to treatment (RC, RP, EE, PE).
  - Best response to treatment (RC / RP, EE, PE).
  - Duration of axitinib treatment.
  - Vital status

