  - Baseline LDH levels  $>1.5 \times \text{ULN}$  (yes vs no). At the beginning of 1st line
  - Baseline Hgb levels  $\leq \text{LLN}$  (yes vs no). At the beginning of 1st line
  - Baseline corrected Ca++ levels  $>10$  mg/dl (yes vs no). At the beginning of 1st line
  - Baseline neutrophil levels  $> \text{ULN}$  (yes vs no). At the beginning of 1st line
  - Baseline platelet levels  $> \text{ULN}$  (yes vs no). At the beginning of 1st line
  - Smoking habits (smoker, non-smoker or former smoker). At the beginning of 1st line
  - Baseline LDH levels  $>1.5 \times \text{ULN}$  (yes vs no). At the beginning of axitinib treatment
  - Baseline Hgb levels  $\leq \text{LLN}$  (yes vs no). At the beginning of axitinib treatment
  - Baseline corrected Ca++ levels  $>10$  mg/dl (yes vs no). At the beginning of axitinib treatment
  - Baseline neutrophil levels  $> \text{ULN}$  (yes vs no). At the beginning of axitinib treatment
  - Baseline platelet levels  $> \text{ULN}$  (yes vs no). At the beginning of axitinib treatment
  - Smoking habits (smoker, non-smoker or former smoker). At the beginning of axitinib treatment

A logistic regression model will then be carried out to study the association between belonging to each of the two extreme treatment response groups, with each of the possible clinical factors of interest, prior to axitinib treatment. That is, those baseline factors (prior to the start with axitinib) that have been studied in section 7 and that are significant ( $P < 0.05$ ) or close to significance ( $P < 0.15$ ).

The factors in this situation will be summarized below, and that potential prognostic factors of the response to axitinib treatment (long responding group vs refractory group) are considered.

---

The optimal model of prognostic factors will be constructed with the variables that are finally significant ( $P < 0.05$ ).

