**- Subpopulation of special interest**

Patients with the sunitinib and axitinib sequence, without liver or bone metastases and MSKCC risk group at the beginning of favorable or intermediate axitinib will be analyzed.

In this group of patients, the following analyzes will be carried out by group (long responders / refractories):

- Best response to treatment (RC, RP, EE, PE).
- Duration of treatment with axitinib (months).
- PFS, PFS will be shown in all patients of this subpopulation, and this same SLP per group
- TRO, clinical benefit.
- Time to progression.
- Overall Survival. OS will be shown in all patients of this subpopulation, and OS per group.

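### Number and site of metastases date from the diagnosis of advanced disease with no time point stated, and the item on two or more sites at axitinib start is left out of the association analysis and the logistic model

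*SAP*

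**What the plan says.** SAP section 6 lists the CRF variables. Individual sites appear once, as "Metastasis site (multi-response question"), under the diagnosis of advanced disease and ahead of first-line treatment. A separate block, "Risk criteria at the initiation of treatment with axitinib", contains "Presence of 2 or more metastatic sites (Yes/No/Unknown"). The same yes/no item is also collected before first line and at axitinib discontinuation.

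SAP section 7 defines "Number of metastatic locations = sum (Lymph nodes, CNS, Hepatic, Pulmonary, Bone, Other"), with no time point. SAP 7.1 then uses the number of locations in three categories (1, 2, 3 or more), with the note "See this definition in section 7 Definitions of variables and objectives". It also uses "Site of metastases (CNS metastases [yes vs no]; lymph nodes [yes vs no]; lung [yes vs no]; liver [yes vs no]; bone [yes vs no"]), again undated. Protocol 7.1 specifies both factors and does not date them either.

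Other risk criteria are dated. SAP 7.1 lists LDH, haemoglobin, calcium, neutrophils, platelets and smoking at first line and again at axitinib start, for example "Smoking habits (smoker, non-smoker or former smoker). At the beginning of axitinib treatment". Logistic candidates are the pre-axitinib factors already studied that reach P<0.05 or come close (P<0.15).

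The special-interest subpopulation in SAP 7.2 is limited to those given sunitinib and then axitinib, and carries a further condition: "without liver or bone metastases and MSKCC risk group at the beginning of favorable or intermediate axitinib will be analyzed".

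**The concern.** The primary objective asks which clinical factors separate long-term responders from primary refractory patients. Disease burden when the drug is started is a natural candidate. Every patient has had at least one earlier line, and the CRF's first listed reason for starting axitinib is progression on the previous line. Progression can add sites, so the record made at the diagnosis of advanced disease may be out of date by then. The one burden measure collected at axitinib start is not among the factors to be tested.

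Two things are at stake. An association with burden at drug start cannot be examined, and the association with the earlier count may be distorted by patients whose sites changed in between. In the special-interest subgroup, a patient who developed liver or bone disease on an earlier line would still count as free of it.

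**Working it through.** The plan states no sample-size or power figure to reproduce, so the check is mainly a trace of variables, with an illustration of size.

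**Trace**

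1. Site-level CRF fields: one, under the diagnosis of advanced disease; none at axitinib start. The check of the third inclusion criterion in SAP 2.1 (Analysis population) also places metastasis location next to the date and stage of advanced disease. No other listed field can feed the section 7 sum.
2. The axitinib-start risk block has ten items. Nine reach the 7.1 analysis at that time point: ECOG, LDH, haemoglobin, calcium, neutrophils, platelets and smoking directly; lymphocytes through the neutrophil/lymphocyte ratio; time from diagnosis to systemic treatment through the IMDC score. The item on two or more sites is in neither the list nor any risk score.
3. Route into the model: candidates come from factors already tested. An item that is not tested has no P value and cannot be selected.
4. Other routes: SAP 9.2 (Other analyses) describes every CRF variable not covered elsewhere, and Table 6.4 in SAP section 10 covers the axitinib-start risk criteria. The comparison of baseline characteristics in SAP 9.2 names clinical history, first-line treatment and other earlier treatments. It could reach the pre-first-line version of the item, but not the axitinib-start version.

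**Illustration of size (all inputs assumed)**

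True share with two or more sites at axitinib start: 50% in long-term responders and 75% in refractory patients. True OR = (0.75/0.25)/(0.50/0.50) = 3. If a fraction m of these patients is recorded with fewer than two sites, the observed share is p(1 − m).

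| Missed: refractory / responders | Observed shares | Observed OR |
|---|---|---|
| 20% / 20% | 60.0% / 40% | 2.25 |
| 40% / 40% | 45.0% / 30% | 1.91 |
| 30% / 20% | 52.5% / 40% | 1.66 |
| 60% / 40% | 30.0% / 30% | 1.00 |
| 20% / 30% | 60.0% / 35% | 2.79 |
| 40% / 60% | 45.0% / 20% | 3.27 |

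Equal under-recording attenuates the OR. Unequal under-recording can remove the association or push it above its true value.

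**Power, second assumed set**

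The protocol expects about 60 patients at about 2:1, so 40 responders and 20 refractory. With true shares of 80% (refractory) and 50% (responders), OR = 4.00 and two-sided 5% power is 62%. Equal under-recording of 20% gives OR 2.67 and power 42%; 40% gives OR 2.15 and power 28%.

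**Precision**

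For OR 3 with 15/20 refractory against 20/40 responders, the standard error of log OR is √(1/15 + 1/5 + 1/20 + 1/20) = 0.606. The 95% interval is exp(1.099 ± 1.96 × 0.606), about 0.92 to 9.8.

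**The case against.** The other side has several good points.

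- A reader might infer that the axitinib-start item is unused. It is not: SAP 9.2 and Table 6.4 have it described. It is missing only from the association list and the model.
- A reader might infer that metastases are measured at the wrong time. The plan does not support that. SAP 7.1 admits any factor from before axitinib, SAP 9.2 counts clinical history as baseline, and Protocol 7.1 attaches the word baseline to ECOG and the laboratory values but not to number or site. The date is also an inference from the CRF list, because the section 7 definition states none and the CRF itself is not reproduced.
- The documents do not show metastatic burden to be a key factor. No risk score in the SAP uses number or site, and the quoted model for previously treated patients dropped liver metastases.
- The illustration is hypothetical, assumes that sites are only ever gained, and runs in both directions. The shift from 3 to 2.25 or 1.9 is small beside an interval of 0.92 to 9.8.
- Replacing number and site with the yes/no item would alter protocol-specified primary factors. Protocol 8.7 says major changes to the primary analyses are reflected in a protocol amendment, and SAP section 1 records that version 3 followed a draft of results.

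All of this limits the claim and the remedy. It does not explain why the closest available burden measure is the only item of its block left out of the comparison.

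**Conclusion.** The point holds in a limited form. Number and site of metastases can only describe the diagnosis of advanced disease, at least one line before axitinib, and the SAP does not say so. Burden at axitinib start was collected as a yes/no item but cannot be tested as planned. The special-interest subgroup combines liver and bone status from the earlier date with an MSKCC group at axitinib start.

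A reader might conclude that the planned analysis necessarily dilutes or hides an association. The documents do not support that, because they give no rate of change in sites and no direction. If under-recording were equal in the two groups at 20% to 40%, a true OR of 3 would be seen as 2.25 to 1.9; if unequal, it could be lower or higher. The prevalences, the true OR and the under-recording rates are all assumptions. The case for changing the SAP rests on the trace: a relevant item already collected is left out of the primary question.

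**What to change.** 1. Add two or more metastatic sites at axitinib start (yes/no) to SAP 7.1 as an additional association factor and logistic candidate. Mark it as added after the draft of results.
2. Keep the protocol-specified number and site factors. In SAP sections 7 and 7.1, label them as recorded at the diagnosis of advanced disease.
3. In the special-interest subpopulation of SAP 7.2, state that liver and bone status is as of that diagnosis while the MSKCC group is at axitinib start.

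The cost is SAP wording and one more table row; no new data are needed. The downsides are one more comparison without multiplicity adjustment, a two-level variable only, and correlation with the number factor in a sample of about 60. The item cannot supply the 1, 2, 3-or-more categories or individual sites at axitinib start. Those would need further chart abstraction, or should be stated as a limitation.

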### Study population

The eligible patient population for this study includes any patient with advanced or metastatic renal cell carcinoma who has been treated with axitinib for at least 9 months or whose best response to this treatment has been DP.

The requirements for a patient's inclusion are:

1. These patients had to receive axitinib as second-line treatment or further line, according to its Summary of Product Characteristics. Two groups exhibiting extreme responses to the drug will be compared: one group of patients showing no evidence of disease progression for at least 9 months after the start of treatment with axitinib versus a group of patients showing disease progression while taking the drug at the first response assessment.
2. Collection of clinical, safety and response data in patients with advanced renal cell carcinoma.

The study is expected to be conducted in at least 30 sites throughout Spain in order to reach the maximum number of study patients.

The study will start at each site after the agreement with the site is signed and all study documentation and information on the procedures and objectives of the study have been received by the person appointed by the sponsor.

Recruitment will be competitive between all participating sites. All the patients at a particular site who meet the inclusion criteria during the recruitment period may be enrolled. The recruitment period will have a maximum of three months from the opening of the last study site. No patient follow-up will be carried out after their inclusion in the study.

Patients will be considered evaluable if they meet the inclusion criteria and do not meet the exclusion criteria, and have received at least one dose of axitinib prior to their inclusion in the study.

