**Analysis population****All analyses will be performed with evaluable patients.**

The CRF contains the information related to the eligibility criteria as binary variable (Yes/No) for each of the described items.

Several of these criteria can be verified with the data recorded in the CRF. This verification is performed in order to prevent the inclusion of non-evaluable participants in the statistical report and prior to the start of any analysis.

These patients will be considered screening failure, and in the statistical report they will thus be included in a table of patient disposition together with the patients screening failure initially confirmed by the sponsor.

The criteria to be verified in the patient CRFs to define the evaluable population are described below:

- An "evaluable" patient must have received at least one dose of axitinib prior to inclusion in the study: it must be verified that the "Starting dose" and the "Treatment start date with axitinib" have been specified in "Treatment with axitinib". This date must be prior to the date of signing the informed consent (for patients who are still alive at enrolment).

- Inclusion requirement *Patients must have received axitinib as second-line treatment or further line*: it must be verified that there is information concerning a first-line treatment in the "First-line treatment" section.

- IC1: *Evidence of a personally signed and dated informed consent document indicating that the patient (or his/her legal representative) has been informed of all relevant aspects of the study. Informed consent will only be obtained from patients who are still alive.*

It must be verified that the date of signing the informed consent is specified (for patients who are still alive at enrolment).

Noted that for patients already dead before the study inclusion, the CII could be "No".

- IC2: *Aged 18 or over.*

It must be verified that the age calculated with respect to the date of the baseline visit is  $\geq 18$  years.

- IC3: *Histologically confirmed diagnosis of advanced renal cell carcinoma, with at least one radiological evaluation of the disease according to RECIST 1.1 criteria.*

It must be verified that the following data have been indicated: Date of first diagnosis, Tumour stage at disease diagnosis, Date of advanced disease diagnosis, Stage of advanced disease, Metastasis location, Best treatment response (first-line treatment).

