- IC4: *Treatment with axitinib, as second-line or further line treatment and with progression-free survival PFS of 9 months or more or with disease progression at the first response assessment.*

It must be verified that in "Treatment with axitinib", "Treatment line in which it has been received" is  $\geq 2$ .

It must be verified that the patient meets one of the following two conditions:

- "*Progression-free survival PFS of 9 months or more*": the time from the start of treatment with axitinib to disease progression or death by any cause is  $\geq 9$  months (see definition of PFS in section 7. Definition of variables).

or

- "*Disease progression at the first response assessment*": PD has been indicated in "Treatment with axitinib/ Best response to treatment".

If there is a contradiction between the binary variables and the information shown in the CRF, the latter shall be assumed valid.

A list of candidate patients who are non-evaluable must be made, and after approval or rectification by the study sponsor/coordinator, the list of non-evaluable patients who will be excluded from the analyses will be closed.

The sponsor will be informed of the number of non-evaluable study patients for the analysis and the reasons for non-inclusion, for consultation and confirmation prior to starting the analyses.

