## **8 MANAGEMENT OF MISSING DATA**

In the event of incomplete dates, proceed as follows:

- If the year XXXX is known, but not the day or month, 15/06/XXXX will be entered.
- If the month YY and year XXXX are known, but not the day, 15/YY/XXXX will be entered.

For all other variables, no criterion for substituting missing data will be used.

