**Inferential analysis:**

When an inferential analysis is required, parametric tests will be used for continuous variables, and non-parametric tests will be used for ordinal, categorical or non-parametric variables. The hypothesis tests to be carried out will be two-tailed test in all cases with a significance level of 0.05. For variables that are not adjusted to a normal (or parametric) distribution, the Mann–Whitney U test (for unpaired data) or the Wilcoxon signed-rank test (for paired data) will be used. The Chi-squared test (or Fisher’s exact test when applicable) shall be used for analysing the contingency tables and for the comparison of proportions and/or frequency distributions.

Survival analyses shall be performed using the Kaplan-Meier method, providing the median, mean, 95% confidence intervals, as well as number of events and number of censored cases.

When it is necessary to compare survival functions, the log-rank test will be used.

The assumptions of normality and homoscedasticity of the variables for the use of parametric tests will be studied.

The level of significance in all the statistical inference tests will be  $\alpha=0.05$ , two-tailed.

Adjustment by multiple comparisons is not planned.

Estimates will be calculated with a 95% confidence level, the SPSS statistical analysis software package, V18.0 or later, will be used.

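### The number of metastatic locations counts all organs written under 'Other, specify' as one, which can place a few patients in too low a level of the 1 / 2 / 3-or-more factor

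*SAP*

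**What the plan says.** SAP section 6, under the diagnosis of advanced disease, lists "Metastasis site (multi-response question" with five named sites (lymph nodes, CNS, liver, lungs, bone) and one further option, 'Other, specify'. No field asks for a number of organs.

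SAP section 7 turns this into a count: "Number of metastatic locations = sum (Lymph nodes, CNS, Hepatic, Pulmonary, Bone, Other".

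SAP section 7.1 analyses the result as "Number of metastatic locations (1, 2 and" three or more. Protocol section 7.1 has the same three levels. Neither document says how several organs written under 'Other, specify' are to be counted.

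Section 6 also records a separate yes/no item on the presence of two or more metastatic sites: before the first line, at the start of axitinib and at its discontinuation.

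**The concern.** The factor is named as a number of locations, but the formula counts ticked options. For any patient with more than one organ under 'Other' the two differ, and always in the same direction. Read literally:

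- Lung, adrenal and pancreas: three organs, score 2.
- Adrenal and contralateral kidney: two organs, score 1. A correctly completed item on two or more metastatic sites would say yes for this patient, so two variables from one CRF would disagree.

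The factor is one of those listed for the primary objective. As a baseline characteristic it can enter the logistic model if it passes the P < 0.15 screen in SAP section 7.1. At stake is a one-way misclassification that puts some patients with more widespread disease into the lower two levels.

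**Working it through.** The plan has no figure to reproduce here. The check has two parts: where the level changes, and how often that could happen.

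**1. Where the level changes**

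Take each of the six options as 0 or 1 (the SAP does not state the coding, but this is the natural reading). There are 2^6 = 64 tick patterns.

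| Sum | Patterns |
|---|---|
| 0 | 1 |
| 1 | 6 |
| 2 | 15 |
| 3 or more | 42 |

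'Other' is ticked in 32 patterns. Let 'Other' now count the organs it holds, two or more.

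- 'Other' alone (1 pattern): level 1 becomes 2, or 3-or-more if three organs are listed.
- 'Other' plus one named site (5 patterns): level 2 becomes 3-or-more.
- 'Other' plus two or more named sites (32 − 6 = 26 patterns): the sum is already at least 3, so the level does not move.

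The level is wrong in 1 + 5 = 6 patterns only.

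**2. How often this could happen**

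From Protocol section 6.1.1, using midpoints where a range is given: lung 55%, bone 35%, liver 35%, CNS 5%. Assumed, because the documents do not give them: lymph nodes 30% to 50%; number of other organs per patient Poisson with mean m = 0.25 to 0.6; sites independent.

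- P(no named site) = 0.45 × 0.65 × 0.65 × 0.95 × (1 − nodes) = 0.126 with nodes 30%, 0.090 with nodes 50%.
- P(exactly one named site) = P(no named site) × the sum of p/(1 − p) over the five sites = 0.352 and 0.303.
- P(at most one named site) = 0.478 and 0.393.
- P(two or more other organs) = 1 − e^(−m)(1 + m) = 0.0265 at m = 0.25, 0.1219 at m = 0.6.

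P(wrong level) is the product of the last two. Dividing by P(at least one site) = 1 − P(no named site) × e^(−m) restricts it to patients with some site recorded.

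| Nodes | m | P(wrong level) | Among patients with a site | Per 60 patients |
|---|---|---|---|---|
| 50% | 0.25 | 1.0% | 1.1% | 0.7 |
| 30% | 0.25 | 1.3% | 1.4% | 0.8 |
| 50% | 0.6 | 4.8% | 5.0% | 3.0 |
| 30% | 0.6 | 5.8% | 6.3% | 3.8 |

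Among patients scored 1 or 2, the share in the wrong level runs from 1.7% to 9.7%. If the share were equal in both groups, the estimated 2:1 ratio (about 40 and 20 of 60) gives 0.4 to 2.5 long-term responders (40 × 1.1% to 40 × 6.3%) and 0.2 to 1.3 refractory patients.

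**The case against.** **A location need not mean an organ.** Neither document defines it so, and the sum of six site categories is a reproducible operational definition. Fair, but the variable is named as a number of locations, and the same CRF asks whether there are two or more metastatic sites. A formula that returns 1 for adrenal plus contralateral kidney does not measure what the factor is called.

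**The reach is narrow and the size is assumed.** Both stand. The top level absorbs most of the undercount, and the decisive input, the mean number of other organs, is in no document. No effect on an odds ratio, a p-value or model selection has been calculated. The study is exploratory and this is one factor among many.

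**Disagreement with the two-or-more-sites item may be real.** Also correct. Metastasis site is recorded at the diagnosis of advanced disease, so a later yes may reflect new metastases.

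**A stronger reading.** A reader might infer that a patient with no option ticked scores 0 and drops out of the factor, which has no level for 0. The documents do not support this as a general result. In SAP section 2.1, the check of inclusion criterion 3 requires certain data to have been indicated, among them "Stage of advanced disease, Metastasis location, Best treatment response (first-line treatment". A patient without a metastasis location is therefore normally screened out before analysis: "A list of candidate patients who are non-evaluable must be made, and after approval or rectification by the study sponsor/coordinator" the list of exclusions is closed. What remains is a smaller matter of consistency. The SAP admits "any patient with advanced or metastatic renal cell carcinoma", and the CRF allows stage III for advanced disease, so an eligible patient may have no metastatic site. The SAP does not say whether such a patient fails the check or, if kept by rectification, which level applies. On missing data other than dates it says only: "For all other variables, no criterion for substituting missing data will be used".

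**Conclusion.** The concern holds in a limited form. The stated formula counts several organs under 'Other, specify' as one. It gives too low a level when 'Other' holds two or more organs and at most one named site is ticked, which is 6 of 64 tick patterns, and it leaves the level unchanged otherwise. The error can only lower the level.

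The share of patients affected cannot be derived from the documents. Under the assumptions above (0/1 coding, independent sites, nodes 30% to 50%, mean 0.25 to 0.6 other organs) it is roughly 1% to 6%, or about 1 to 4 of 60. This is a minor issue in an exploratory study, worth correcting because the correction is cheap. It does not show that the primary comparison is materially biased, nor that patients are lost from the factor through a score of 0.

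**What to change.** In SAP section 7, define the number of metastatic locations as the number of named sites ticked plus the number of distinct organs listed under 'Other, specify'. Have that text coded before the group comparison by someone who does not see response group. Query a patient whose count contradicts the item on two or more metastatic sites, using only the record made before the first line, because the later records may reflect new metastases.

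Separately, add a sentence that reconciles the study population, the check of inclusion criterion 3, the CRF stage options and the factor levels, so that it is clear how an eligible advanced (stage III) patient with no metastatic site is handled.

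Cost: two SAP sentences and manual coding of one free-text field in about 60 CRFs. No new data are needed beyond answers to any queries. The downside is some judgement in coding free text, for example whether two entries name the same organ.
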